8.4.3.1. Exposure During Pregnancy

For both unapproved/unlicensed products and for marketed products, an exposure during pregnancy (EDP) occurs if:

- A female becomes, or is found to be, pregnant either while receiving or having been exposed (eg, because of treatment or environmental exposure) to the investigational product; or the female becomes or is found to be pregnant after discontinuing and/or being exposed to the investigational product;
- An example of environmental exposure would be a case involving direct contact with a Pfizer product in a pregnant woman (eg, a nurse reports that she is pregnant and has been exposed to chemotherapeutic products).

- A male has been exposed (eg, because of treatment or environmental exposure) to the investigational product prior to or around the time of conception and/or is exposed during his partner's pregnancy.

If a subject or subject's partner becomes or is found to be pregnant during the subject's treatment with the investigational product, the investigator must report this information to Pfizer Safety on the CT SAE Report Form and an EDP supplemental form, regardless of whether an SAE has occurred. In addition, the investigator must submit information regarding environmental exposure to a Pfizer product in a pregnant woman (eg, a subject reports that she is pregnant and has been exposed to a cytotoxic product by inhalation or spillage) to Pfizer Safety using the EDP supplemental form. This must be done irrespective of whether an AE has occurred and **within 24 hours** of awareness of the exposure. The information submitted should include the anticipated date of delivery (see below for information related to termination of pregnancy).

Follow-up is conducted to obtain general information on the pregnancy and its outcome for all EDP reports with an unknown outcome. The investigator will follow the pregnancy until completion (or until pregnancy termination) and notify Pfizer Safety of the outcome as a follow-up to the initial EDP supplemental form. In the case of a live birth, the structural integrity of the neonate can be assessed at the time of birth. In the event of a termination, the reason(s) for termination should be specified and, if clinically possible, the structural integrity of the terminated fetus should be assessed by gross visual inspection (unless pre-procedure test findings are conclusive for a congenital anomaly and the findings are reported).

If the outcome of the pregnancy meets the criteria for an SAE (ie, ectopic pregnancy, spontaneous abortion, intrauterine fetal demise, neonatal death, or congenital anomaly [in a live-born baby, a terminated fetus, an intrauterine fetal demise, or a neonatal death]), the investigator should follow the procedures for reporting SAEs.

Additional information about pregnancy outcomes that are reported to Pfizer Safety as SAEs follows:

- Spontaneous abortion includes miscarriage and missed abortion;
- Neonatal deaths that occur within 1 month of birth should be reported, without regard to causality, as SAEs. In addition, infant deaths after 1 month should be reported as SAEs when the investigator assesses the infant death as related or possibly related to exposure to the investigational product.

Additional information regarding the EDP may be requested by the sponsor. Further follow-up of birth outcomes will be handled on a case-by-case basis (eg, follow-up on preterm infants to identify developmental delays). In the case of paternal exposure, the investigator will provide the subject with the Pregnant Partner Release of Information Form to deliver to his partner. The investigator must document in the source documents that the

subject was given the Pregnant Partner Release of Information Form to provide to his partner.

8.4.3.2. Exposure During Breastfeeding

Scenarios of exposure during breastfeeding must be reported, irrespective of the presence of an associated SAE, to Pfizer Safety **within 24 hours** of the investigator's awareness, using the CT SAE Report Form. An exposure during breastfeeding report is not created when a Pfizer drug specifically approved for use in breastfeeding women (eg, vitamins) is administered in accord with authorized use. However, if the infant experiences an SAE associated with such a drug's administration, the SAE is reported together with the exposure during breastfeeding.

8.4.3.3. Occupational Exposure

An occupational exposure occurs when, during the performance of job duties, a person (whether a healthcare professional or otherwise) gets in unplanned direct contact with the product, which may or may not lead to the occurrence of an AE.

An occupational exposure is reported to Pfizer Safety **within 24 hours** of the investigator's awareness, using the CT SAE Report Form, regardless of whether there is an associated SAE. Since the information does not pertain to a subject enrolled in the study, the information is not recorded on a CRF; however, a copy of the completed CT SAE Report Form is maintained in the investigator site file.

8.4.4. Medication Errors

Other exposures to the investigational product under study may occur in clinical trial settings, such as medication errors.

Safety Event	Recorded on the CRF	Reported on the CT SAE Report Form to Pfizer Safety Within 24 Hours of Awareness
Medication errors	All (regardless of whether associated with an AE)	Only if associated with an SAE

8.4.4.1. Medication Errors

Medication errors may result from the administration or consumption of the investigational product by the wrong subject, or at the wrong time, or at the wrong dosage strength.

Medication errors include:

- Medication errors involving subject exposure to the investigational product;
- Potential medication errors or uses outside of what is foreseen in the protocol that do or do not involve the participating subject.

Such medication errors occurring to a study participant are to be captured on the medication error page of the CRF, which is a specific version of the AE page.

In the event of a medication dosing error, the sponsor should be notified immediately.

Whether or not the medication error is accompanied by an AE, as determined by the investigator, the medication error is recorded on the medication error page of the CRF and, if applicable, any associated AE(s), serious and non-serious, are recorded on an AE page of the CRF.

Medication errors should be reported to Pfizer Safety **within 24 hours** on a CT SAE Report Form **only when associated with an SAE**.

9. DATA ANALYSIS/STATISTICAL METHODS

Detailed methodology for summary and statistical analyses of the data collected in this study is outlined here and further detailed in a statistical analysis plan (SAP), which will be maintained by the sponsor. The SAP may modify what is outlined in the protocol where appropriate; however, any major modifications of the primary endpoint definitions or their analyses will also be reflected in a protocol amendment.

9.1. Sample Size Determination

A sample size of approximately 24 subjects with varying degrees of hepatic function (6 subjects per cohort) will provide 90% confidence interval to detect a 2-fold change in exposure (AUC_{inf}) with 80% tolerance probability. Table 4 presents the precision of the estimated effects with the associated width of 90% confidence intervals with increasing standard deviation.

Table 4. Precision for 2-fold Change in AUC_{inf} as Function of Assumed Variability

Level of Precision	Assumed SD* = 0.16 CCI	Assumed SD* = 0.23 CCI	Assumed SD* = 0.28 CCI
n=6/cohort	18% (1.65; 2.43)	24% (1.51; 2.64)	29% (1.42; 2.81)

*SD = Standard Deviation calculated on natural logarithmic scale

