Appendix 1. Abbreviations68
Appendix 2. Child-Pugh Classification (CPC) of Liver Dysfunction71

PROTOCOL SUMMARY

Background and Rationale:

The current study is designed to evaluate the effect of varying degrees of hepatic impairment on the plasma pharmacokinetics of PF-05221304.

Objectives and Endpoints:

[figure not shown]
Primary Objective:	Primary Endpoints:
To compare the pharmacokinetics of PF-05221304 (both total and unbound) following administration of a single oral dose in adult subjects with varying degrees of hepatic impairment relative to age- and body weight-matched subjects without hepatic impairment.	PF-05221304 PK parameters derived from plasma: 
 C_{max}, AUC_{inf}, f_u, $C_{max,u}$, and $AUC_{inf,u}$.
Secondary Objectives:	Secondary Endpoints:
To compare additional pharmacokinetic parameters (both total and unbound) of PF-05221304 following administration of a single oral dose in adult subjects with varying degrees of hepatic impairment relative to age- and body weight-matched subjects without hepatic impairment.	PF-05221304 PK parameters derived from plasma: 
 T_{max}, AUC_{last}, $AUC_{last,u}$, CL/F, CL_u/F, V_z/F, $V_{z,u}/F$ and $t_{1/2}$, as data permit.
To evaluate the safety and tolerability of a single oral dose of PF-05221304 when administered to adult subjects with varying degrees of hepatic impairment relative to age- and body weight-matched subjects without hepatic impairment	Assessment of treatment-emergent adverse events, clinical laboratory tests, vital signs, and 12-lead ECGs.

CCI

Study Design:

This is a non-randomized, open-label, single-dose, parallel-cohort, multisite study with overall design summarized below.

090177e190d319bb\Approved\Approved On: 29-Apr-2019 07:31 (GMT)

Study Treatment:

The investigational product is PF-05221304, provided as tablets, each containing 25 mg active drug. A single, oral, 25 mg dose of PF-05221304 will be administered with a standard morning meal.

Statistical Method:

A sample size of approximately 24 subjects with varying degrees of hepatic function (6 subjects per cohort) will provide enough precision to determine the 90% confidence interval to detect a 2-fold change in exposure (AUC_{inf}) with 80% tolerance probability between each of the Test (impaired) cohorts and the Reference (without hepatic impairment) cohort.

SCHEDULE OF ACTIVITIES:

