3. STUDY DESIGN

3.1. Study Overview

This is a non-randomized, open-label, single-dose, parallel-cohort, multisite study to investigate the effect of varying degrees of hepatic impairment on the plasma pharmacokinetics (total and unbound) of PF-05221304 after a single oral 25 mg dose administered in the fed state. A total of approximately 24 subjects with varying degrees of hepatic function will be enrolled into the study to ensure that up to 6 evaluable subjects in each of the 4 hepatic function cohorts complete the study. Subjects will be selected based on their Child-Pugh score as shown in Table 1.

Table 1. Hepatic Function Categories Based on Child Pugh Score

Cohort	Description	Child-Pugh Score	Number of Subjects
1	Without hepatic impairment	Not Applicable	6 ^a
2	Mild hepatic impairment	Class A (5 to 6 points)	6
3	Moderate hepatic impairment	Class B (7 to 9 points)	6
4	Severe hepatic impairment	Class C (10 to 15 points)	6 ^b

[figure not shown]
a. Additional subjects *may* be dosed to a maximum of 10 subjects to ensure mean age is ± 5 years and mean body weight ± 10 kg of this cohort is in line with pooled average assessed when $\geq 75\%$ of subjects are dosed across other 3 cohorts.

b. If recruitment across the sites selected proves to be prohibitive, study will dose only 4 subjects in this cohort.

Child-Pugh scores will be determined as described in [Appendix 2](#), at the screening visit. Recruitment for subjects meeting the criteria for Cohorts 3 and 4 will initiate first. Recruitment for subjects in Cohort 2 will start when approximately 50% of total subjects across Cohorts 3 and 4 (ie, 6 of 12) have been dosed. Subjects in Cohort 1 will be recruited last to match the average demographics (at a minimum, age and weight; and as much as practically possible gender) across the pooled Cohorts 2 through 4. Approval from the Sponsor must be garnered *before* proceeding with dosing subjects in Cohort 1.

The overall study design is summarized below in [Figure 1](#). For individual subjects, the total duration of participation from the Screening Visit to the on-site Follow-up Visit (Day 7) will be a minimum of approximately 3 weeks and a maximum of approximately 5 weeks.

Figure 1. C1171006 Study Design

In this study, subjects who prematurely discontinue for non-safety related reasons may be replaced, at the discretion of the principal investigator (PI) and Sponsor study team.

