9.3.3. Statistical Methods

The effect of varying degrees of hepatic impairment on PK parameters will be assessed by constructing 90% confidence intervals around the estimated difference between each of the Test (impaired) cohorts and the Reference (without hepatic impairment) cohort using a one-way ANOVA model based on natural log transformed data.

One-way analysis of variance (ANOVA) will be used to compare the natural log transformed PF-05221304 AUC_{inf} , AUC_{last} and C_{max} , unbound AUC_{inf} ($AUC_{inf,u}$), unbound AUC_{last} ($AUC_{last,u}$), and unbound C_{max} ($C_{max,u}$), as data permit, for each of the hepatic impairment classification cohorts (Test) to the cohort without hepatic impairment (Reference). Estimates of the adjusted mean differences (Test-Reference) and corresponding 90% confidence intervals will be obtained from the model. The adjusted mean differences and 90% confidence intervals for the differences will be exponentiated to provide estimates of the ratio of adjusted geometric means (Test/Reference) and 90% confidence intervals for the ratios.

CCI

[figure not shown]
The PF-05221304 PK parameters C_{max} , AUC_{last} , AUC_{inf} , f_u , T_{max} , $t_{1/2}$, CL/F , V_z/F , $AUC_{inf,u}$, $AUC_{last,u}$, $C_{max,u}$, CL_u/F , and V_{zu}/F will be summarized descriptively by hepatic function cohort. Individual PF-05221304 concentrations will be listed and summarized descriptively by nominal PK sampling time and hepatic function cohort. Individual subject and summary profiles (median and means) of the concentration-time data will be plotted by treatment for both total plasma PF-05221304 and unbound PF-05221304. For summary statistics and summary plots by sampling time, the nominal PK sampling time will be used; for individual subject plots by time, the actual PK sampling time will be used. PF-05221304 AUC_{inf} , AUC_{last} , C_{max} , $AUC_{inf,u}$, $AUC_{last,u}$, and $C_{max,u}$ individual subject parameters will be plotted by hepatic function cohort.

Linear regression may be used to analyze the potential relationship between appropriate PK parameters (eg CL/F and V_z/F) and hepatic function (eg, serum albumin concentration, or prothrombin time). Estimates of the slope and intercept, together with their precision (90% confidence interval [CI]), and the coefficient of determination will be obtained from the model.

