4.2. Statistical Decision Rules

No decision rules are planned.

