10. APPENDICES

Appendix 1. SAS CODE FOR ANALYSES

/* Letter assignments for cohort within the estimate statement in the code below are as follows;

A = Severe (Test)
 B = Moderate (Test)
 C = Mild (Test)
 D = Normal (Reference);
 */;

For ANOVA: An example of the PROC GLM code is provided below:

```
proc glm data=tab.pk;
  class cohort;
  model l&var = cohort / ss3 clparm alpha=0.1;
  lsmeans cohort;
  estimate 'Severe vs Normal'      cohort 1 0 0 -1;
  estimate 'Moderate vs Normal'    cohort 0 1 0 -1;
  estimate 'Mild vs Normal'        cohort 0 0 1 -1;
  ods output Estimates = est&var;
  ods output FitStatistics = fit&var;
  ods output ModelANOVA = tst&var;
  ods output OverallANOVA = overall&var;
run;
```

[figure not shown]
For ANCOVA: An example of the PROC GLM code is provided below:

```
proc glm data=tab.pk;
  class cohort;
  model l&var = cohort age weight / ss3 clparm alpha=0.1;
  lsmeans cohort;
  estimate 'Severe vs Normal'      cohort 1 0 0 -1;
  estimate 'Moderate vs Normal'    cohort 0 1 0 -1;
  estimate 'Mild vs Normal'        cohort 0 0 1 -1;
  ods output Estimates = est&var;
  ods output FitStatistics = fit&var;
  ods output ModelANOVA = tst&var;
  ods output OverallANOVA = overall&var;
run;
```

CCI

090177e190d319bc\Approved\Approved On: 29-Apr-2019 07:33 (GMT)

090177e190d319bc\Approved\Approved On: 29-Apr-2019 07:33 (GMT)

CCI

090177e190d319bc\Approved\Approved On: 29-Apr-2019 07:33 (GMT)

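### Does Table 4 misstate the precision, given a four-cohort ANOVA and a severe cohort that may stop at 4?

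*Protocol*

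**What the plan says.** Protocol section 9.1 states: "A sample size of approximately 24 subjects with varying degrees of hepatic function (6 subjects per cohort) will provide 90% confidence interval", for a 2-fold change in AUCinf with 80% tolerance probability. Table 4 has a single row, for 6 per cohort: 18% (1.65; 2.43) at SD 0.16, 24% (1.51; 2.64) at SD 0.23 and 29% (1.42; 2.81) at SD 0.28, the SDs being on the natural log scale. The Statistical Method paragraph of the Protocol Summary repeats the claim, again for 6 per cohort, "with 80% tolerance probability between each of the Test (impaired) cohorts and the Reference (without hepatic impairment) cohort".

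Two footnotes to Table 1 (Protocol section 3.1, repeated in SAP section 2.1) let the cohort sizes move. For the severe cohort: "If recruitment across the sites selected proves to be prohibitive, study will dose only 4 subjects in this cohort". The reference cohort may grow; additional subjects may "be dosed to a maximum of 10 subjects to ensure mean age is" and mean body weight are in line with the pooled impaired cohorts.

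For the analysis, Protocol section 9.3.3 says: "One-way analysis of variance (ANOVA) will be used to compare the natural log transformed PF-05221304" exposure parameters, "constructing 90% confidence intervals around the estimated difference between each of the Test (impaired) cohorts" and the reference cohort. The code in SAP Appendix 1 fits all four cohorts in one model, "model l&var = cohort / ss3 clparm alpha=0.1", and takes each impaired-versus-normal contrast from it. SAP section 4.1 plans no hypothesis test, and section 4.2 adds: "No decision rules are planned".

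**The concern.** Table 4 is the only justification of the sample size, and two things about it look wrong.

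First, its intervals do not come from the planned model. One ANOVA on 24 subjects in four cohorts has 24 − 4 = 20 error degrees of freedom. The printed limits match a stand-alone comparison of two cohorts of 6, with 10. Section 9.1 does not say which basis it uses.

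Second, the severe cohort is the only impaired cohort allowed to shrink, and section 1.3.3 says that very limited clinical data exist on severe impairment for comparably cleared compounds. A reader who takes the 80% figure as applying to every impaired cohort whatever its size would expect more precision for the severe comparison than 4 subjects give. If the loss were large, the study could end with a severe-to-normal ratio too imprecise to use for dosing recommendations, with no warning in the protocol.

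**Working it through.** **Inputs.** 90% two-sided interval, 80% tolerance, true ratio 2, SDs 0.16 / 0.23 / 0.28 and 6 per cohort (Protocol section 9.1); 4 severe subjects or up to 10 controls (Table 1 footnotes); four-cohort model (SAP Appendix 1).

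**Formula.** The log-scale half-width that is not exceeded with 80% probability is

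h = t(0.95, df) × SD × √(1/n1 + 1/n2) × √(χ²(0.80, df)/df).

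The limits are 2·exp(±h), and the printed percentage is 1 − exp(−h).

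**Step 1: reproduce Table 4.** Take 6 v 6 and df = 6 + 6 − 2 = 10. Then t = 1.8125, √(1/6 + 1/6) = 0.5774 and √(13.442/10) = 1.1594, so h = 1.2132 × SD.

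| SD | h | 1 − exp(−h) | Limits | Printed |
|---|---|---|---|---|
| 0.16 | 0.1941 | 17.6% | 1.647–2.428 | 18% (1.65; 2.43) |
| 0.23 | 0.2790 | 24.3% | 1.513–2.644 | 24% (1.51; 2.64) |
| 0.28 | 0.3397 | 28.8% | 1.424–2.809 | 29% (1.42; 2.81) |

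All nine entries match. In a scan of 4 to 30 degrees of freedom at 6 v 6, only 10 reproduces them all. The table contains no arithmetic error.

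**Step 2: planned ANOVA, 6 per cohort.** With df = 20, t = 1.7247 and √(25.038/20) = 1.1189, so h = 1.1141 × SD. The limits are 1.67–2.39 / 1.55–2.58 / 1.46–2.73, narrower than printed at every SD. The probability that the ANOVA interval is no wider than Table 4 is

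P[χ²(20) ≤ 20 × (1.2132/(1.7247 × 0.5774))²] = P[χ²(20) ≤ 29.69] = 0.925.

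The SD cancels, so this holds in all three columns.

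**Step 3: severe cohort of 4, controls at 6, planned ANOVA.** With cohorts of 4, 6, 6 and 6, df = 22 − 4 = 18. Then t = 1.7341, √(1/4 + 1/6) = 0.6455 and √(22.760/18) = 1.1245, so h = 1.2586 × SD. That is 1.2586/1.2132 = 1.037, or 3.7% wider on the log scale than Table 4.

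| SD | Printed (6 v 6) | 4 v 6, planned ANOVA |
|---|---|---|
| 0.16 | 1.65–2.43 | 1.64–2.45 |
| 0.23 | 1.51–2.64 | 1.50–2.67 |
| 0.28 | 1.42–2.81 | 1.41–2.85 |

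The largest shift is 2.85 − 2.81 = 0.04. The Table 4 widths are met with probability P[χ²(18) ≤ 18 × (1.2132/(1.7341 × 0.6455))²] = P[χ²(18) ≤ 21.15] = 0.728. Simulation with 400,000 draws gives 0.727 to 0.729.

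**Step 4: scale.** Within Table 4, going from SD 0.16 to SD 0.28 moves the upper limit by 2.81 − 2.43 = 0.38, more than nine times the largest effect of losing two severe subjects.

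**Step 5: larger reference cohort.** With 4 severe subjects, the planned ANOVA meets the Table 4 widths with probability 79.6% at 7 controls, 84.7% at 8 and 91.1% at 10.

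**Step 6: two-cohort basis at 4 v 6.** With df = 8, the limits are 1.60–2.51 / 1.45–2.77 / 1.35–2.97, and the Table 4 widths are met with probability 58.3%. The documents plan no such interval.

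**The case for a change.** The best case for a change is that precision is the whole justification here. A reader should therefore be able to see the expected width for every cohort size that the protocol allows. The reduction to 4 is written into the design, and the conservatism of the two-cohort figures does not fully absorb it: 72.8% falls short of 80% even under the more favourable planned model. On Table 4's own two-cohort basis the figure is 58.3%. Growth of the reference cohort would close the gap, but it is permitted only for age and weight matching and cannot be counted on for precision. The remedy would be one table row and a sentence.

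Much of this stands as fact. The degrees of freedom are not stated, there is no row for 4, and extra controls are not planned for precision. What does not stand is the inference that the plan claims too much. Both 80% statements carry the condition of 6 subjects per cohort, and no sentence promises 80% at 4. The 58.3% describes an analysis that nobody will run. The 72.8% measures the fallback against widths that the protocol prints as an illustration, not as a requirement.

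**Conclusion.** No change follows: the missing detail is real, but supplying it would gain nothing. Table 4 is correct at its stated size and errs on the cautious side for the planned ANOVA (92.5% against the stated 80%). A two-cohort variance is a reasonable planning basis, since it does not borrow degrees of freedom from the other two cohorts, and the basis can be recovered from the printed figures.

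The fallback to 4 severe subjects is disclosed in both documents. It applies only if recruitment proves prohibitive, and under the planned model it moves the 80%-tolerance limits by 0.04 at most. Under the model's assumptions the reported 90% interval keeps its nominal coverage at 4, and its actual width will be there to read. With no hypothesis, decision rule or required width, no result or conclusion would differ. Naming the degrees of freedom would be a courtesy to the reader, not a correction.

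The figures assume a common SD across cohorts and an estimable AUCinf in every subject used; the ANOVA figures for 4 severe subjects also assume the mild and moderate cohorts at 6. A markedly larger SD in severe impairment would matter more than the choice of degrees of freedom, and an extra row in Table 4 under a common SD would not show it.
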